Dmochowski 2010 ³⁸	At each FU visit and as clinically indicated	Not described	100u: 36% 200u: 48%
Denys 2012 ⁶²	At each FU visit and as clinically indicated	Positive dip confirmed by culture	100u: 4.8% 150u: 9.1%
Tincello 2012 ⁵⁷	At each FU visit and as clinically indicated	Not described	200u: 30%
Chapple 2013 ³⁶	At each FU visit and as clinically indicated	Urine microscopy $>5/\text{hpf}$ + $>10^3$ cfu	100u: 24%
Nitti 2016 ³⁷	At each FU visit and as clinically indicated	Not described	100u: 13-17%

Table 4: Rates of Urinary Retention Following Botox A and Mid-Urethral Sling

	Botox Dose	Time Point	How Defined	Retention Rate
MID-URETHRAL SLING				
ESTEEM	NA	At baseline and 2 weeks postop	No specific PVR cutoff	7% in both groups (sling vs sling ± BPTx) Catheter after 2 weeks: 2% in both groups
TOMUS Richter, 2010 ⁴⁷	NA	Baseline and 12 months	ISC after 6 weeks or surgery for obstructed voiding	3.6% (TVT) vs. 0.6% (TOT)
Barber, 2008 ⁵³	N/A	Baseline and 12 months	ISC after 6 weeks or surgery for obstructed voiding	4.7% (TVT) vs. 2.6% (TOT)
BOTOX A				
ROSETTA ³³	200 u	At baseline and every FU visit	PVR>300 ml or PVR>200 ml and symptoms of incomplete voiding	ISC: 2wks (16%), 1m (8%), 3m (4%), 6m (2%), any visit (20%)
ABC ³⁵	100 u	At baseline and every FU visit	PVR>300 ml or PVR> 150 ml and symptoms of incomplete voiding	ISC: 2wks (9%), 1m (3%), 2m (5%), 4m (3%), 6m (1%) PVR > 150 ml: 2wks (30%), 1m (27%), 2m (20%), 4m (15%), 6m (7%)
Dmochowski 2010 ³⁸	100 u 200 u	At baseline and every FU visit	> 200 ml	100u: 14.5%, 200u: 28% ISC: 100u: 11%, 200u: 21%
Denys 2012 ⁶²	100 u 150 u	At baseline and every FU visit	> 200 ml, need for ISC	very low
Tincello 2012 ⁴⁰	200 u	Not specified	Need for ISC	ISC: 14-16%
Chapple 2013 ³⁶	100 u	Not specified	ISC at PVR > 200 ml	6.9%
Nitti 2016 ³⁷	100 u	Not specified	Need for ISC	ISC 4%

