To address the issue of postoperative sling revision, the team developed a plan for several potential scenarios which may require the surgeon to revise the sling, detailed below. Women who undergo a sling revision will all be considered as having “additional treatment” regardless of indication. The reason for sling revision will be documented.

1. Urinary retention / incomplete bladder emptying (abnormal PVR) – An abnormal post-void residual is defined as PVR > 150 cc in this protocol (consistent with exclusion criteria). This is a known complication after mid-urethral sling. In the ESTEEM trial, the rate of sling revision was low (only one subject in each arm underwent sling revision). Similarly, Barber’s trial which included 70% women with MUI, the sling revision rate was 0-1%, which is also consistent with the TOMUS trial. For retention/incomplete emptying, the postoperative management and need for sling revision will be left up to the surgeon’s clinical judgment.
2. Worsening OAB/lower urinary tract symptoms with a normal PVR – it is possible that some women may experience worsening OAB symptoms immediately postoperatively. It is unclear from the literature in which women such symptoms may be transient and ultimately resolve once postoperative recovery is complete, or in which women it will persist and/or worsen over time. Therefore, for women with a normal PVR complaining of worsening OAB symptoms, sling revision will be deferred until 3 months postoperatively. This will provide important information about the natural course of these symptoms in the immediate postoperative period following sling. If after 3 months the patient desires sling revision due to worsening OAB symptoms, the surgeon can perform the procedure based on his/her clinical judgment. There is no evidence to support any potential harm by delaying sling revision in a woman with OAB symptoms and a normal PVR.
3. Persistent SUI symptoms – For women who have persistent SUI symptoms, sling revision/replacement can be performed after 3 months based on the surgeon’s clinical judgment.

5.2 *Botox Injection*

5.2.1 *Surgeon Certification*

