5.3.2 Postoperative Visits and Procedures

Patients will undergo clinical and PRO assessments at 2-weeks, 3 months, and 6 months postoperatively (See **Table 9**). The primary outcome will be at 6 months.

Table 9: Timeline of Visits, Events, and Data Collection

	Screening	Baseline	Procedure (Botox or Sling) ^{‡, **}	1-2 Week Visit ^{**}	Telephone Call	3 Month Visit	Botox reinjection ^{‡, **}	1-2 Week Visit ^{**}	Telephone Call	6 Month Visit [†]
Window	1-4 w	1-4 w			1w before 3m visit	2 w pre – 4 w post			1w before 6m visit	2 w pre – 4 w post
Consent	X									
Coordinator visit	X	X		X	X	X		X	X	X
Hx/PE	X	X				X				X
Urodynamics**		X								
Medication and other treatment audit	X	X				X				X
Preg test~**			X				X			
Urine dip~**	X	X	X	X		X	X	X		X
PVR	X	X		X		X		X		X
Adverse Events			X	X		X	X	X		X
PGSC						X				X
UDI		X				X				X
Bladder diary		X			Diary reminder	X			Diary reminder	X
PRO/Questionnaires Varies by milestone.		X		X		X		X		X

[†] primary outcome visit

* all subjects will undergo a post-op visit for PVR/urine dip 2 weeks after Botox A or sling procedure

[‡] standard of care visit

** must be done in clinic

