Rate of Urinary Tract Infection (UTI) Events	Dichotomous 1=yes 0=no	The frequency of acute UTI events will be taken from all adverse event reporting forms submitted for a participant. The outcome variable will be coded with a value of "Yes" if the participant had any reported acute UTIs over their study duration, identified by MEDRA coding preferred term of "Urinary tract infection" and "recurrent" is NOT specified by verbatim adverse event term or comments. If no acute UTI events were reported for a participant, the outcome variable will be coded with a value of "No".Final database lock review took efforts to query sites for participants with questionable urine test results and get PI confirmation that all necessary events had been reported.
Rate of recurrent Urinary Tract Infection (UTI) Events	Dichotomous 1=yes 0=no	The frequency of recurrent UTI events will be taken from all adverse event reporting forms submitted for a participant. The outcome variable will be coded with a value of "Yes" if the participant had any reported recurrent UTIs over their study duration, identified by MEDRA coding preferred term of "Urinary tract infection" and "recurrent" is specified by verbatim adverse event term or comments. If no recurrent UTI events were reported for a participant, the outcome variable will be coded with a value of "No". Final database lock review took efforts to query sites for participants with questionable urine test results and get PI confirmation that all necessary events had been reported.
Rate of Urinary Retention Events	Dichotomous 1=yes 0=no	The frequency of urinary retention events will be taken from all adverse event reporting forms submitted for a participant. The outcome variable will be coded with a value of "Yes" if the participant had any reported urinary retention over their study duration,

Variable	Туре	Definition
		identified by MEDRA coding preferred term of "Urinary retention". If no urinary retention events were reported for a participant, the outcome variable will be coded with a value of "No".
		Final database lock review took efforts to query sites for participants with reported self- catheterization logs or questionable post void residual results (>200mL, aside from visits immediately post-surgery) and get PI confirmation that all necessary events had been reported.

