Rate of AE of "residual Urine Volume"	Dichotomous 1=yes 0=no	The frequency of residual urine volume events will be taken from all adverse event reporting forms submitted for a participant. The outcome variable will be coded with a value of "Yes" if the participant had any reported residual urine events over their study duration, identified by MEDRA coding preferred term of "Residual urine volume". If no residual urine volume events were reported for a participant, the outcome variable will be coded with a value of "No".
		Final database lock review took efforts to query existing adverse events with terms such as "incomplete bladder emptying", "sensation of incomplete bladder emptying" for any post void residual assessments completed around the time of the event. Details from query responses helped with MEDRA coding the relevant level of severity ("Urinary Retention" vs. "Residual urine volume") accurately.
Complications after study intervention And Complication after cross- over study intervention	Dichotomous 1=yes 0=no	The frequency of complications after study intervention will be taken from Surgeon's Report forms submitted for a participant, for both the main study treatment and allowed Botox reinjection if applicable. The outcome variable for each specific complication will be coded with a value of "Yes" if ever reported over their study duration, otherwise it will be coded with a value of "No". If a participant experienced any complication after main study interventions, the composite indicator will be coded with a value of "Yes", otherwise coded to "No".
Bladder Injury Ureteral Injury		The frequency of complications after cross-over study intervention will be taken from any Off Protocol Surgeon's Report forms submitted for a participant The outcome

Variable	Туре	Definition	
Urethral Injury Vaginotomy		variable for each specific complication will be coded with a value of "Yes" if ever reported over their study duration, otherwise it will be coded with a value of "No". If a participant experienced any complication after a crossover study intervention, the composite indicator will be coded with a value of "Yes", otherwise coded to "No".	
		Note that all reported intervention complications are expected to have an accompanying adverse event form entered but may not be recorded as an adverse event to reduce database redundancy.	

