10.2 Adverse Events/Complications/Adverse Symptoms

MUSA complications are divided into "adverse symptoms" and "adverse events".

Participants were asked to report any adverse events or adverse symptoms from randomization through 12 months follow-up. All adverse events were collected on an adverse event log and coded using MedDRA (V24.0). In addition, a few adverse symptoms are captured as part of the PRO questionnaires.

Adverse symptoms will be captured using an active approach using validated questionnaires and an open-ended approach.

- a. Active capture for specific patient-reported adverse symptoms will be identified by responses on validated questionnaires These 3 adverse symptoms are patient report of new or worsening: 1) pelvic/vaginal pain, 2) sensation of incomplete bladder emptying (based on UDI responses) and 3) dyspareunia (based on PISQ-IR response). These are captured at 3, 6, 9, and 12 months.
- b. Open-ended capture for adverse symptoms will also be captured using the open-ended approach and recorded on the AE log. Symptoms of interest include: 1) New/worsening partner dyspareunia and 2) New/worsening constipation. Using the open-ended approach, symptoms are captured if reported by the participant and documented on the Adverse Event log.

Adverse events will be captured using the standard AE open-ended capture approach using chart review, physician report, or patient report corroborated by medical documentation and recorded on the Adverse Event log.

A table summarizing the Adverse Events and Adverse symptoms of interest is as follows (all variable definitions are included in Section 9.2):

Postoperative complications	
Adverse symptom	Definition
*New/worsening abdominal/genital pain at or beyond 3 month visit	UDI item N captured at 3, 6, 9, and 12 months and per patient report, chart review, physician report
*New/worsening dyspareunia at or beyond 3 month visit	PISQ item C5 captured at 3, 6, 9, and 12 months and per patient report, chart review, physician report
*New/worsening report of difficulty emptying bladder at or beyond 3 months	UDI item J captured at 3, 6, 9, and 12 months and per patient report, chart review, physician report
New/worsening partner dyspareunia at or beyond 3 month visit	Per patient report, chart review, physician report

Adverse Event	
Postop need for catheter and/or ISC at or beyond 2 weeks (sling or Botox)	Captured by chart review, physician report, exam, or patient report corroborated by medical documentation

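### Post-void residual is measured on schedule in both arms, but the SAP defines no analysis of it, so a raised residual with no catheter, adverse-event form or later symptom worsening is not counted

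*SAP*

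**What the plan says.** **Collection.** Protocol Table 9 and the SAP 4.6 flow chart schedule PVR at baseline, 2 weeks, 3 months and 6 months in both arms. The protocol states that "all subjects will undergo a post-op visit for PVR/urine dip 2 weeks after Botox A or sling procedure". The SAP adds PVR at the Botox reinjection visit and 2 weeks after it. There is none at the 9- and 12-month calls.

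**Outcomes touching bladder emptying (SAP 9.2 and 10.2).** There are four:

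- Urinary retention: "The frequency of urinary retention events will be taken from all adverse event reporting forms submitted for a participant", identified by MedDRA preferred term. Where no urinary "retention events were reported for a participant, the outcome variable will be coded with a value of 'No".
- Residual urine volume: also from adverse-event forms by preferred term, with the same default. At lock, existing events with related wording were queried: "Details from query responses helped with MEDRA coding the relevant level of severity".
- Catheter placement or self-catheterization from 2 weeks after the procedure: from self-catheterization (CISC) logs plus adverse-event entries.
- Self-reported symptom, UDI item J: "New/worsening report of difficulty emptying bladder at or beyond 3 months".

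**Check on the retention outcome.** Sites were queried for women with a CISC log or with "questionable post void residual results (>200mL, aside from visits immediately post-surgery) and get PI confirmation".

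**Volume cutoffs.** Protocol 5.1.3 says "An abnormal post-void residual is defined as PVR > 150 cc in this protocol (consistent with exclusion criteria". The reinjection criteria (protocol 5.2.3, SAP 4.4) require PVR below 200 mL, and the label text in protocol 7.5.3 and 7.5.4 also uses 200 mL.

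**The concern.** Retention is a known harm of both treatments, and protocol 3.4.3.c lists its rate as an outcome. The trial takes an objective measurement of emptying at the same visits in both arms, then reports the harm from forms whose existence depends on someone deciding to file one. A measured high value with no form becomes an explicit No, not a missing value.

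The gap is widest at 2 weeks. UDI item J starts at 3 months, and the catheter outcome sees only women who catheterize. In the protocol's own source data, measured PVR and catheter use differ most early on. The group left out also matters for another safety outcome: the label text in protocol 7.5.5 gives a urinary tract infection incidence of 44% with maximum PVR above 200 mL against 23% below it.

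**Working it through.** **Step 1: which planned outcome sees a raised PVR at 2 weeks in a woman who does not catheterize?**

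| Outcome or check | Source | Does it see her? |
|---|---|---|
| Retention event | Adverse-event form | Only if a form was filed and so coded |
| Residual-volume event | Adverse-event form; lock query began from existing events | Only if a form was filed |
| Catheter or self-catheterization | CISC log, adverse-event entries | No |
| UDI item J | Questionnaire at 3, 6, 9, 12 months | Only if her bother is worse than at baseline at 3 months or later |
| Lock-time query | CISC log, or PVR >200 mL outside the exempted visits | Only if PVR is >200 mL and the 2-week visit is not exempt; a form must still follow |

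The woman missed by every row has a raised PVR, no catheter, no form and no later symptom worsening. Values of 151 to 200 mL trigger no query by volume at any visit.

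**Step 2: is measured PVR summarised elsewhere?** SAP 9.2, section 10 and the display list in section 15 contain no PVR variable, threshold or table. Measured PVR serves eligibility, reinjection, the lock-time queries and help with MedDRA coding. The SAP gives no volume that separates the two preferred terms.

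**Step 3: illustration of size.** There is no figure in the plan for this point to reproduce. The denominator is the planned 73 per arm: 69 / 0.95 = 72.6, rounded up to 73, as in SAP section 6. The rates come from protocol Table 4, 100 units only.

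- ABC trial: "PVR > 150 ml: 2wks (30%), 1m (27%), 2m (20%), 4m (15%), 6m (7"%. Catheterizing was 9% at 2 weeks and 1% at 6 months. Only these two time points match common MUSA visits.
- Placebo-controlled dose-ranging trial: 14.5% under a >200 mL definition and 11% catheterizing, with no time point attached to the rates.

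Expected women = 73 × rate:

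| Source | Raised PVR | Catheterizing | Difference |
|---|---|---|---|
| ABC, >150 mL, 2 weeks | 73 × 0.30 = 21.9 | 73 × 0.09 = 6.6 | 15.3 |
| ABC, >150 mL, 6 months | 73 × 0.07 = 5.1 | 73 × 0.01 = 0.7 | 4.4 |
| Dose-ranging, >200 mL | 73 × 0.145 = 10.6 | 73 × 0.11 = 8.0 | 2.6 |

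So about 3 to 15 of 73 women (3.5% to 21%) would have a raised PVR and no catheter, depending on source and cutoff. This assumes that the cited rates carry over to MUSA and that the women catheterizing are among those with raised PVR. It is the size of the group that rests on forms or later symptoms, not the number missed.

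**The case against.** The strongest reply is that emptying is already covered. The stated aim concerns catheterization for voiding dysfunction, and the catheter outcome answers it using CISC logs as well as forms. UDI item J is active patient report in both arms. The lock query is triggered by any CISC log, whatever the volume. No protocol outcome list names PVR as an endpoint, and a PVR table would include elevations without symptoms. SAP sections 2 and 15 already allow extra analyses and displays. All of this stands, and it narrows the gap to the group in Step 1. But permission to add a table does not specify one, and it leaves the cutoff open to later choice.

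A reader might infer four stronger things that the documents do not support:

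- *Retention is under-reported.* A route to under-reporting is shown. Neither its occurrence nor its size is.
- *The query skips the 2-week visit, or differs by arm.* The exempted visits are undefined: they could be the day of the procedure or the 2-week check, and surgery may or may not include the injection. The exemption limits only the query; early events on forms still count.
- *Unmasked sites decide.* Surgeons and participants are unmasked, but outcome assessors are masked (SAP 4.5.1), and the documents do not say who files these forms.
- *The trial could separate the arms on PVR but not on forms.* Setting 30% against the 7% sling retention rate from ESTEEM in Table 4 mixes definitions, since that rate has no stated PVR cutoff. Catheter rates are not form rates either, and safety p-values are descriptive only (SAP 7.8, 10.1), so power is not a useful yardstick.

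The 200 mL query also has a basis in the protocol, through the reinjection criteria and label text. The conflict is between passages, not a plain error in the query.

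**Conclusion.** The point holds as an omission. A scheduled, objective measure of a main known harm of both treatments has no planned analysis, and the form-based outcomes default to No. The other two emptying outcomes reduce the gap but do not close it, least of all at 2 weeks. Emptying problems may therefore be under-reported, by an amount and in a direction between arms that cannot be known from the documents. The 3 to 15 women per 73 is an illustration from two cited trials under the assumptions stated with it. The Botox arm also has extra PVR checks around reinjection, so the opportunity for detection is not equal. Adding the analysis is a worthwhile, low-cost improvement; the primary efficacy analysis is unaffected.

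**What to change.** Add to SAP 9.2 and section 10 one descriptive safety table of measured PVR, by arm and common scheduled visit (2 weeks, 3 months, 6 months). It should give:

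- the number measured, and the median and interquartile range;
- the proportions above 150 mL and above 200 mL, both values already in the documents;
- the risk difference between arms with a 95% confidence interval.

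Show values from the reinjection visit and the 2-week check after it separately, because only the Botox arm has them. Keep the retention and residual-volume rates as a second line labelled site-reported. State which visits the lock-time query exempts and whether this applies to both procedures. Reconcile the 150 and 200 mL passages; the table reports both so that no clinical cutoff has to be chosen here.

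The cost is SAP wording and one table, with no new visit or data. The drawback is that the table counts asymptomatic elevations, so its rates may exceed the form-based ones and the caption should say so. Because the SAP already reports findings from the lock review, label the table as added at that stage.

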3.1.2 Exploratory Aims

Exploratory aims of this study (consolidated from the main protocol and the 12-month addendum) are the following:

- 1. **12-month aim:** To compare the effectiveness of intradetrusor injection of 100 units of Botox A to mid-urethral sling for change in MUI symptoms 12 months following treatment
- 2. Secondary urinary outcomes: To compare treatment with Botox A to treatment with mid-urethral sling for improving the number of urinary incontinence episodes on bladder diary 6 and 12 months post-treatment.
- 3. **Predictors of poor treatment response:** To develop models to identify baseline predictors of change of MUI, OAB, and SUI outcomes measured using the UDI, between baseline and 6 and 12 months post-treatment.
- 4. **Quality of life and global impression:** To compare quality of life outcomes and Patient Global Impression-Improvement (PGI-I), Patient Global Impression-Severity (PGI-S) between groups randomized to Botox A versus mid-urethral sling 6 and 12 months post-treatment.
- 5. **Safety and additional treatments:** To describe rates of reoperation (sling revision) after mid-urethral sling and intermittent catheterization due to voiding dysfunction/partial urinary retention after Botox A detrusor injection, to compare the proportion of women in each group with UTI and recurrent UTI, rates of other serious and non-serious adverse events, and to compare the proportion of women in each group initiating additional (off protocol) treatment other than Botox A and mid-urethral sling for SUI and/or OAB.
- 6. **Cost-effectiveness analysis:** To determine the cost effectiveness of Botox A injection versus mid-urethral sling for the treatment of MUI symptoms on an intent-to-treat basis 6 and 12 months post-treatment.
- 7. **UDI MID:** To explore MIDs for UDI total score and stress and irritative subscores for this MUI population.

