AEs will be listed and summarized by system organ class and preferred event term. Summaries will be of the number of events and number of individuals experiencing events by treatment group and will be created for all AEs, and AEs by severity. If a complete onset date is unknown and it cannot be confirmed that the event occurred during this time period, then the event will be considered a treatment-emergent AE.

Reported adverse events will be reviewed to identify terms meeting definitions for events or symptoms of interest The review will be conducted via keyword searches through reported event terms and comments for specific events (e.g. vaginal mesh exposure, ER visits, etc.) and by preferred term and system/organ class for more general complications (e.g. new/worsening vaginal infection, other infections, etc.).

Worsening symptoms will be assessed by identifying worsening responses (compared to baseline) to the specific patient-questionnaire items identified at post-baseline collection times.

Post-operative complications will be summarized by complication type. Summaries will be the number of individuals experiencing complications by treatment group.

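### SAP 9.2 is contradictory on whether procedure complications enter the adverse event log, so the all-AE and severity tables may undercount them

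*SAP*

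**What the plan says.** SAP 9.2 defines indicators for bladder injury, ureteral injury, urethral injury and vaginotomy, plus a composite for any complication. Their source is fixed: "The frequency of complications after study intervention will be taken from Surgeon's Report forms submitted for a participant". This covers the main treatment and the permitted Botox reinjection. A parallel set for cross-over procedures comes from the Off Protocol Surgeon's Report.

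The same entry ends with a note on how these records relate to adverse events. It first says that "all reported intervention complications are expected to have an accompanying adverse event form entered". It then says that they "may not be recorded as an adverse event to reduce database redundancy".

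SAP 10.2 describes one MedDRA-coded adverse event log as the place where adverse events are collected, and plans the general summaries from it: "AEs will be listed and summarized by system organ class and preferred event term". Counts of events and of individuals by treatment group "will be created for all AEs, and AEs by severity".

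The safety aim in SAP 3.1.2 names several specific harms and then adds "rates of other serious and non-serious adverse events".

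**The concern.** The two halves of the note cannot both be the working rule. If each complication has an adverse event form, there is nothing to leave out. If some are left off to avoid duplication, the log is incomplete for harms that arise during the procedure, and every summary built from the log alone inherits the gap.

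This matters because the trial compares an operation with an office injection. Injury at the procedure is one of the ways in which the two treatments may differ in harm. An any-AE or severity table that leaves out some of these injuries would still be read as a full account. Protocol 7.9 defines adverse events broadly, as untoward medical events linked in time to study participation, and makes no exception for events already held on another form.

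**Working it through.** No complication rate, adverse event rate or count of unlogged events appears in the documents, so there is no planned figure to reproduce for this point. The check is a comparison of the text, followed by an illustration under stated assumptions.

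**Which source feeds which summary**

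| Summary | Source | Includes a complication held only on the Surgeon's Report? |
|---|---|---|
| Four injury indicators and composite (SAP 9.2) | Surgeon's Report, Off Protocol Surgeon's Report | Yes |
| All AEs by system organ class and preferred term; AEs by severity (SAP 10.2) | Adverse event log | No merge step described |
| Any AE both unexpected and related (SAP 9.2) | Fields on the adverse event form | No merge step described |
| SAEs (SAP 10.3; Protocol 7.4; Serious AE row in SAP 4.6) | SAE reporting, no exemption for complications | Not shown to be affected |

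**Is there a reconciliation step?** SAP 9.2 describes checks at lock for other harms. A sling removal found on the Additional Therapy form led to a request for an adverse event form. Sites were queried about urinary tract infection, retention and catheterization. No such check is described for the four procedure injuries.

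**Where would they be shown?** SAP 10.2 plans a summary of post-operative complications by type and treatment group. However, its table of events and symptoms of interest lists none of the four injuries, and the display list in SAP 15 has no separate complications table.

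**Illustration of size**

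Inputs:
- Women per arm: 73 (SAP 6: 69/0.95 = 72.6, rounded up to 73). This is the number randomized; the safety population counts treated women and may be slightly smaller.
- b, the share of sling-arm women with any logged adverse event: 20% to 50% (assumption).
- c, the share with a procedure complication, independent of other adverse events: 2% to 10% (assumption).
- s, the share of complications that reach the log: 0 in the worst case, 1 if the expectation in SAP 9.2 is met.

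Undercount of the any-AE percentage = (1 − b) × c × (1 − s).

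- One woman with an unlogged complication and no other adverse event: 1/73 = 1.4 percentage points.
- s = 0, b = 50%, c = 2%: 0.50 × 0.02 = 1.0 point (50.0% shown, 51.0% with complications).
- s = 0, b = 30%, c = 5%: 0.70 × 0.05 = 3.5 points (30.0% against 33.5%).
- s = 0, b = 20%, c = 10%: 0.80 × 0.10 = 8.0 points (20.0% against 28.0%).
- s = 1, any b and c: 0.

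A woman who already has another logged adverse event does not change the any-AE percentage. She does change the event counts and, if the complication is her most severe event, possibly the severity table.

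**The case against.** The strongest reply is that nothing is lost. The injuries are safety outcomes in their own right, with an indicator each and a composite, for both arms, for reinjection and for cross-over. The stated motive, avoiding redundancy, implies that the event is already in the database. The note also expects an adverse event form, and if sites comply the undercount is zero. The aim concerns other adverse events beyond the named harms, and safety p-values are descriptive (SAP 7.8 and 10.1).

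Most of this stands, and it rules out several stronger readings that a reader might infer:

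- **That these harms vanish from all reporting.** They do not; SAP 9.2 analyses them separately.
- **That complications are in fact left out.** The text says only that they may be, and no count is given.
- **That SAE totals lose cases.** Nothing exempts a serious complication from SAE reporting. Protocol 7.4 requires it, SAP 10.3 defines an SAE as any event that meets the criteria, and SAP 4.6 lists a Serious AE form of its own. What is missing is only a described check of the surgeon's report complications against those criteria.
- **That the sling is made to look safer.** Protocol 7.5.1 names bladder perforation as specific to sling placement, so a larger undercount in that arm is plausible. But Protocol 7.5.2 also states a risk of injury for Botox injection, and no rates by arm are given.

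What the reply does not answer is that separate indicators leave the all-AE and severity tables incomplete, and that the SAP does not fix where the separate results will be shown.

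**Conclusion.** The point holds in a limited form. The SAP contradicts itself on whether procedure complications are recorded as adverse events, and it describes no step that would make the log-based summaries complete. The all-AE tables, the severity tables and the indicator for unexpected and related events may therefore omit some procedure injuries. For that last indicator, an omission matters only if the complication would have been judged both unexpected and related.

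The size is unknown. It is zero if every complication is logged. Otherwise it is about 1.4 points for each affected woman with no other adverse event, and about 1 to 8 points under the assumed ranges with none logged. Those ranges are assumptions, not figures from the documents. The direction is plausibly towards undercounting the sling arm, by inference only. No error rate is affected, and the efficacy analyses are untouched. The correction is worth making because it replaces a stated rule that can make a safety comparison incomplete, using data already collected.

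**What to change.** 1. Rewrite the note in SAP 9.2 so that it states one rule on whether an intervention complication is recorded as an adverse event.
2. Build the all-AE and severity tables, and the indicator for unexpected and related events, from the union of the adverse event log and the complications on the Surgeon's Report and Off Protocol Surgeon's Report. Match on participant and date so that each event counts once, and code the added records in MedDRA. Flag cross-over complications, so that an injury at a later procedure is not read as caused by the treatment first received.
3. At lock, check these complications against the SAE criteria in SAP 10.3, as a confirmation that SAE reporting is complete.
4. Keep the separate complications summary, name the four injuries in the SAP 10.2 table, and add the display to SAP 15.

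The cost is a small merge and the coding of the added records. If the surgeon's report forms do not hold severity, expectedness and relatedness (the documents do not show their fields), those would need a site query. Adverse event totals would be slightly higher. No new participant data are needed.
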